### **6.3.3. Blinding of the Sponsor**

Those study team members who are involved in ensuring that protocol requirements for study intervention handling, allocation, and administration are fulfilled at the site (eg, study manager; CRAs and unblinded medical monitor) will be unblinded for the duration of the study. All other study team members and all laboratory personnel performing the serology assays will remain blinded to vaccine assigned/received throughout the study.

### **6.3.4. Breaking the Blind**

The study will be participant-, participant's parent(s)/legal guardian(s)-, and investigator-blinded.

The IRT will be programmed with blind-breaking instructions. In case of an emergency, the investigator has the sole responsibility for determining if unblinding of a participant's treatment assignment is warranted. Participant safety must always be the first consideration in making such a determination. If the investigator decides that unblinding is warranted, the investigator should make every effort to contact the sponsor prior to unblinding a participant's treatment assignment unless this could delay further management of the participant. If a participant's treatment assignment is unblinded, the sponsor must be notified within 24 hours after breaking the blind. The date and reason that the blind was broken must be recorded in the source documentation and the CRF.

## **6.4. Study Intervention Compliance**

All doses of investigational product will be administered by the appropriately designated unblinded study staff at the investigator site. The date and time of each dose administered in the study site will be recorded in the source documents and recorded in the CRF. The administration route (SC or IM) of study intervention and study participant identification will be confirmed at the time of dosing by an unblinded member of the study site staff.

## **6.5. Concomitant Therapy**

### **6.5.1. Prohibited Concomitant Vaccines and Treatments**

- Receipt of any investigational vaccines, drugs, or medical devices is prohibited during study participation.
- Receipt of nonstudy pneumococcal vaccine is prohibited during study participation.
- Receipt of blood/plasma products, immunoglobulins, and/or immunosuppressive therapy (including a  $\geq 14$ -day course of systemic corticosteroids) is prohibited through Visit 6.

### **6.5.2. Permitted Concomitant Vaccines and Treatments**

#### **Specified concomitant vaccines**

Consistent with the vaccination schedule recommended by the Japan Pediatric Society, specified concomitant vaccines containing Hib, HepB, rotavirus, diphtheria, tetanus, acellular

pertussis, polio virus, measles, rubella, and varicella antigens will be administered concomitantly with the relevant dose of investigational product. The vaccination schedule of the specified concomitant vaccines are shown in Table 1.

**Table 1. Vaccination Schedule for Investigational Product and Specified Concomitant Vaccines**

Visit Number	Visit 1	Visit 2	Visit 3	Visit 5
IP Vaccination a	Dose 1	Dose 2	Dose 3	Dose 4
Visit Window	2 through 6 Months of Age	4 to 8 Weeks After Visit 1	4 to 8 Weeks After Visit 2 (Completed by 12 Month of Age)	12 to 15 Months of Age (≥60 Days After Dose 3)
Investigational Product (20vPnC or 13vPnC)	X	X	X	X
Specified concomitant vaccines				
Hib vaccine	X (Vax 1)	X (Vax 2)	X (Vax 3)	X (Vax 4)
Hep B vaccine b	X (Vax 1)	X (Vax 2)		
Rotavirus vaccine	X (Vax 1)	X (Vax 2)	X c (Vax 3)	
DTaP-IPV b		X (Vax 1)	X (Vax 2)	X (Vax 4)
MR combination vaccine d				X (Vax 1)
Varicella vaccine d				X (Vax 1)

Abbreviation: DTaP-IPV = diphtheria, tetanus, acellular pertussis, inactivated polio combination vaccine, Hep B = hepatitis B, Hib = *Haemophilus influenzae* type b, MR = measles and rubella, Vax = vaccination

- Doses of vaccines to be administered at visits 1 to 3 will be preferred to be administered at 2, 3, and 4 months of age consistent with the recommended vaccination schedule.
- Dose 3 of DTaP-IPV and Hep B vaccine will be administered according to the vaccination schedule defined in the labeling. These vaccines will be administered between the blood sample collection 1 month after Dose 3 (Visit 4) and 14 days before Dose 4 (Visit 5).
- Dose 3 for penta-valent rotavirus vaccine only.
- Dose 2 of MR combination vaccine and varicella vaccine will be administered according to the vaccination schedule defined in the labeling.

### **Other Concomitant Vaccines and Treatments**

- Influenza vaccine is permitted at any time during influenza season in this study.
- Other nonprohibited licensed age appropriate vaccines may be given between the blood sample collection 1 month after Dose 3 (Visit 4) and 14 days before Dose 4 (Visit 5) for inactivated vaccines or 28 days before Dose 4 (Visit 5) for live vaccines, according to vaccination schedule recommended by the Japan Pediatric Society. Following the blood sample collection performed 1 month after Dose 4 (Visit 6), all licensed vaccines are permitted.

- Use of topical anesthetic is permitted.
- The use of prophylactic antipyretic/pain medication, while permitted, is not recommended on the day prior to vaccination or the day of investigational product administration.
- Inhaled/nebulized, topical (skin, eyes, or ears), or localized injections of corticosteroids (eg, intra-articular or intrabursal administration) are permitted during participant participation in the study.
- Prescription and nonprescription medications, vitamins, minerals, and herbal remedies are permitted during the study.

### **6.5.3. Recording Prior and Concomitant Vaccines and Treatments**

The name and date of administration for all vaccinations should be collected from the time of signing of the ICD to Visit 6 and will be recorded in the CRF. At Visit 1, information on prior vaccinations will also be recorded in the CRF. Vaccines required by the protocol, as well as those not stipulated, will be recorded throughout study participation.

Medications taken to treat SAEs or NDCMCs from the signing of informed consent to the final visit will be recorded in the CRF.

### **6.6. Dose Modification**

Not applicable.

### **6.7. Intervention After the End of the Study**

No intervention will be provided to study participants after the end of the study.

## **7. DISCONTINUATION OF STUDY INTERVENTION AND PARTICIPANT DISCONTINUATION/WITHDRAWAL**

### **7.1. Discontinuation of Study Intervention**

Participant eligibility must be confirmed at each visit (for the vaccination visit, prior to each vaccination) in order to continue in the study.

If a participant no longer meets the eligibility criteria during the vaccination period of the study, further vaccinations should be discontinued, but the participant may remain in the study. If a participant is discontinued from vaccination and the participant's parent(s)/legal guardian(s) consents, safety follow-up will be conducted as per [Section 8.3](#) (AEs and SAEs will be collected for 1 month after the last study vaccination).

See the [SoA](#) for data to be collected at the time of intervention discontinuation and follow-up and for any further evaluations that need to be completed.

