## 3. OBJECTIVES, ESTIMANDS, AND ENDPOINTS

Primary Safety Objective	Estimands	Primary Safety Endpoints

 
To describe the safety profile of 20vPnC by both SC injection and IM injection
 
	
In participants receiving at least 1 dose of investigational product and having safety data reported after any vaccination:
 
 
The percentage of participants reporting prompted local reactions at injection site of investigational product within 7 days after each vaccination in each group
 
The percentage of participants reporting prompted systemic events within 7 days after each vaccination in each group
 
The percentage of participants reporting AEs from Dose 1 to 1 month after Dose 3 in each group
 
The percentage of participants reporting AEs from Dose 4 to 1 month after Dose 4 in each group
 
The percentage of participants reporting SAEs up to 1 month after Dose 4 in each group
 
The percentage of participants reporting NDCMCs up to 1 month after Dose 4 in each group
 
	
 
Prompted local reactions (redness, swelling, and pain at the injection site)
 
Prompted systemic events (fever, decreased appetite, drowsiness/increased sleep, and irritability)
 
AEs
 
SAEs
 
NDCMCs
 

Primary Immunogenicity Objectives	Estimands	Primary Immunogenicity Endpoints
For 20vPnC SC group:		

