### **7.2.1. Withdrawal of Consent**

Participant's parent(s)/legal guardian(s) who request to discontinue receipt of study intervention will remain in the study and must continue to be followed for protocol-specified follow-up procedures. The only exception to this is when a participant's parent(s)/legal guardian(s) specifically withdraws consent for any further contact with him or her or persons previously authorized by the participant to provide this information. Participant's parent(s)/legal guardian(s) should notify the investigator in writing of the decision to withdraw consent from future follow-up, whenever possible. The withdrawal of consent should be explained in detail in the medical records by the investigator, as to whether the withdrawal is only from further receipt of study intervention or also from study procedures and/or posttreatment study follow-up, and entered on the appropriate CRF page. In the event that vital status (whether the participant is alive or dead) is being measured, publicly available information should be used to determine vital status only as appropriately directed in accordance with local law.

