### **8.3.1. Time Period and Frequency for Collecting AE and SAE Information**

The time period for actively eliciting and collecting AEs and SAEs ("active collection period") for each participant begins from the time the participant's parent(s)/legal guardian(s) provides informed consent, which is obtained before the participant's participation in the study (ie, before undergoing any study-related procedure and/or receiving investigational product), through and including Visit 4, and from Visit 5 to Visit 6. Between Visit 4 and Visit 5, only SAEs and NDCMCs will be reported.

Follow-up by the investigator continues throughout and after the active collection period and until the event or its sequelae resolve or stabilize at a level acceptable to the investigator, and Pfizer concurs with that assessment.

For participants who are screen failures, the active collection period ends when screen failure status is determined.

If the participant withdraws from the study and also withdraws consent for the collection of future information, the active collection period ends when consent is withdrawn.

If a participant definitively discontinues or temporarily discontinues study intervention because of an AE or SAE, the AE or SAE must be recorded on the CRF and the SAE reported using the Vaccine SAE Reporting Form.

Investigators are not obligated to actively seek AEs or SAEs after the participant has concluded study participation. However, if the investigator learns of any SAE, including a death, at any time after a participant has completed or withdrawn early from the study, and he/she considers the event to be reasonably related to the study intervention, the investigator must promptly report the SAE to Pfizer using the Vaccine SAE Reporting Form.

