Specific vaccines containing Hib, HBV, rotavirus, diphtheria, tetanus, acellular pertussis, and poliovirus antigens will also be administered concomitantly with Doses 1 to 3 (Visit 1, Visit 2, and Visit 3) in the upper arm or orally (in the case of rotavirus vaccine) consistent with the vaccination schedule recommended by the Japan Pediatric Society. Specific vaccines containing Hib, diphtheria, tetanus, acellular pertussis, poliovirus, measles, rubella, and varicella antigens will be administered concomitantly with Dose 4 (Visit 5) in the upper arm(s) consistent with the vaccination schedule recommended by the Japan Pediatric Society. Prompted local reactions (redness, swelling, and pain at the 20vPnC SC and IM or 13vPnC SC injection site), systemic events (fever, decreased appetite, drowsiness/increased sleep, and irritability), and use of antipyretic/pain medications occurring within 7 days after each vaccination will be collected via a provided e-diary (or e-diary application). AEs, including nonserious AEs, will be collected from the signing of informed consent to 1 month after Dose 3 (Visit 4) and from Dose 4 (Visit 5) to 1 month after Dose 4 (Visit 6). SAEs and NDCMCs will be collected for the entire duration of the study.

Blood will be collected 1 month after Dose 3 (Visit 4), immediately prior to Dose 4 (Visit 5), and 1 month after Dose 4 (Visit 6) to assess immunogenicity.

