#### 6.1.1.4. Serious Adverse Events and Newly Diagnosed Chronic Medical Conditions

##### 6.1.1.4.1. Main Analyses

- Estimands:
  - The percentage of participants reporting SAEs from Dose 1 to 1 month after Dose 4 ([Section 2.1](#)).
  - The percentage of participants reporting NDCMCs from Dose 1 to 1 month after Dose 4 ([Section 2.1](#)).
- Analysis set: Safety population ([Section 4](#)).
- Analysis time point: Dose 1 to 1 month after Dose 4.
- Analysis methodology: Descriptive statistics.
- Reporting results: The numerator (n) and the denominator (N) used in the percentage calculation, the percentage (%), and the corresponding 2-sided 95% CI for participants reporting any SAEs/NDCMCs, each system organ class, and each preferred term within system organ class will be presented by vaccine group. SAEs and NDCMCs will be presented separately.

CCI

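### Protocol Section 7.1 gives infants taken off vaccination a shorter SAE follow-up than the other sections and the primary SAE endpoint require, and does not mention NDCMCs

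*Protocol*

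**What the plan says.** Protocol Section 7.1 covers an infant who no longer meets the eligibility criteria: "further vaccinations should be discontinued, but the participant may remain in the study". If the parents consent, safety follow-up is to follow Section 8.3, and a bracket adds: "AEs and SAEs will be collected for 1 month after the last study vaccination". NDCMCs are not named there.

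The other passages on collection have no such limit:

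- Protocol Section 7.2.1 says that infants whose parents ask to stop study intervention "will remain in the study and must continue to be followed for protocol-specified follow-up procedures".
- Protocol Section 8.3.1, part of the section to which 7.1 points, sets active collection from consent to Visit 4 and from Visit 5 to Visit 6. It adds: "Between Visit 4 and Visit 5, only SAEs and NDCMCs will be reported". It names two early ends to the active period: screen failure, and withdrawal of consent to future data. Coming off vaccination is not one of them.
- SAP Section 2.2 says "SAEs and NDCMCs will be collected for the entire duration of the study". SAP Section 3.1.1.5 repeats this, from the signing of consent to study end.

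The primary safety estimands in Protocol Section 3 include "The percentage of participants reporting SAEs up to 1 month after Dose 4 in each group" and "The percentage of participants reporting NDCMCs up to 1 month after Dose 4 in each group". SAP Section 6.1.1.4.1 analyses "The percentage of participants reporting SAEs from Dose 1 to 1 month after Dose 4", and likewise NDCMCs, as n/N in the safety population. Under SAP Section 4 that population needs one dose and some safety follow-up, not Dose 4. SAP Section 5.3 imputes only partial AE start dates and assay values below the LLOQ.

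**The concern.** A site cannot follow all of these rules for the same infant. Section 7.1 is the passage written for infants taken off vaccination, so a site could reasonably apply its bracket. It also sends the site to the Schedule of Activities for what to collect at discontinuation, but that table shows only Visits 1 to 6.

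If the bracket is applied, SAEs more than 1 month after the last dose are not actively collected, although the infant stays in N for a window that runs on for months. An SAE that is never recorded then counts as no event.

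The missing follow-up may also be informative. The trigger in 7.1 is loss of eligibility, and the exclusion criteria in Section 5.2 include seizure, serious chronic disorder and immunodeficiency. Read literally, infants stopped for such reasons get 1 month of follow-up, while infants stopped at their parents' request get all of it. SAEs are a primary safety endpoint in the first study of 20vPnC given subcutaneously.

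**Working it through.** **Step 1. Reproduce the plan's own safety figure.** Protocol Table 7 gives the probability of at least one event with N = 222. The formula 1 − (1 − p)^222 gives 67.1%, 89.3% and 96.5% for p = 0.5%, 1.0% and 1.5%. The table states 67%, 89% and 97%, so it reproduces. It treats all 222 infants as observed for the whole window.

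**Step 2. Stopping unrelated to risk.** Let d be the share of infants off vaccination but still in the study, and f the fraction of the window observed under the 1-month rule. With a constant event rate,

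reported rate = true rate × [1 − d(1 − f)].

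The documents do not give d, so 1% to 10% is an assumed range. The only loose guide is the 66 of 666 infants (9.9%) allowed as not evaluable after Dose 3 for any reason. The plan gives participation as about 7 to 14 months. I take f from 1/14 (stopped after Dose 1, 14-month stay) to 4/7 (an illustrative late stop in a 7-month stay).

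| d | Infants per group (222 × d) | Factor at f = 1/14 | Factor at f = 4/7 |
|---|---|---|---|
| 1% | 2.2 | 0.991 | 0.996 |
| 2% | 4.4 | 0.981 | 0.991 |
| 5% | 11.1 | 0.954 | 0.979 |
| 10% | 22.2 | 0.907 | 0.957 |

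The extremes are 1 − 0.01 × 3/7 = 0.996 and 1 − 0.10 × 13/14 = 0.907, a relative understatement of about 0.4% to 9%. In the worst row a true 1.0% is reported as 0.91%, and the Table 7 probabilities become 63.6%, 86.8% and 95.2%.

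**Step 3. Stopping related to risk.** Take the preferred schedule of Doses 1 to 3 at 2, 3 and 4 months of age. Dose 4 at 12 to 15 months plus a Visit 6 window of 28 to 42 days puts study end at about 13 to 16.4 months of age. The missed share of the window is

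m = 1 − (months from Dose 1 to last dose + 1)/(end age − 2).

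- Stopped after Dose 1: 1 − 1/11 = 90.9% to 1 − 1/14.4 = 93.1%.
- Stopped after Dose 3: 1 − 3/11 = 72.7% to 1 − 3/14.4 = 79.2%.

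If stoppers have k times the event rate, the share of all events missed is dkm/(dk + 1 − d). Here m runs from 72.7% to 93.1%, and both d and k are assumptions.

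- d = 5%, k = 1: 0.05m = 3.6% to 4.7%.
- d = 2%, k = 3: (0.06/1.04)m = 4.2% to 5.4%.
- d = 5%, k = 3: (0.15/1.10)m = 9.9% to 12.7%.
- d = 10%, k = 3: (0.30/1.20)m = 18% to 23%.

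These are shares of events. The endpoint counts infants with at least one event, so the loss in the reported percentage is smaller wherever a stopper has already been counted.

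**The case against.** The strongest reply is that the documents do not plan to truncate. The sentence in 7.1 defers to Section 8.3, which has no 1-month limit, and the SAP assumes collection to study end. This stands. A reader might infer that the protocol definitely stops SAE collection, but the text shows a contradiction, and lost data is only one way that sites could resolve it.

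Four stronger readings also fail:

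- **NDCMCs are cut off too.** The bracket limits AEs and SAEs only. On NDCMCs Section 7.1 is silent, and the general rules still apply to them. The fault is an omission.
- **The infants who stop because of an SAE are lost.** They are already in the SAE numerator, since Section 8.3.1 requires the event that led to stopping to be recorded. Later, different events would still be missing from the system organ class and preferred term rows.
- **Every late SAE becomes a non-event.** Section 8.3.1.1 has SAEs reported to the sponsor after the active period if the investigator learns of them. This is passive, and Section 8.3.1.2 requires CRF recording only for the active period, so it softens the problem without removing it.
- **Between-group contrasts are biased.** SAEs and NDCMCs are summarised by group, and no between-group difference is visible for them. Redacted text follows this analysis in the SAP, so other supporting analyses cannot be ruled out.

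The affected group is also narrow. Section 7.2.1 covers parent-requested stopping, and after withdrawal of consent no rule collects further data. What remains is mainly infants who lose eligibility and stay in the study.

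**Conclusion.** The inconsistency is real and should be corrected. If the bracket in Section 7.1 is followed, the primary SAE percentage is understated, because infants whose later SAEs are not actively collected stay in the denominator without imputation. No time-at-risk adjustment is visible in the unredacted text.

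The documents cannot fix the size, because they give no stopping share. The understatement is about 0.4% to 9% in relative terms for 1% to 10% stopping unrelated to risk. It could be larger if stopping is related to risk: about 10% to 13% of events in the case of 5% stopping with three times the rate. All of this assumes a constant event rate and sites that apply the bracket.

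Two related gaps belong with this point. The endpoint's end date is undefined for an infant who never receives Dose 4. The AE endpoint from Dose 1 to 1 month after Dose 3 would also be cut short for infants stopped after Dose 1 or 2. The post-Dose 4 AE endpoint is unaffected, since the SAP restricts it to infants who received Dose 4. The noninferiority tests and sample size are untouched.

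**What to change.** Reconcile Protocol Section 7.1 with Sections 7.2.1 and 8.3.1 and with SAP Sections 2.2 and 3.1.1.5. For infants off vaccination whose parents have not withdrawn consent, state that SAEs and NDCMCs, both named, are collected to the scheduled Visit 6 time, by telephone if needed. The 1-month limit should then apply at most to nonserious AEs.

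In the SAP, define the end of the SAE and NDCMC window for infants who never receive Dose 4, for example as the scheduled Visit 6 time. An added exposure-adjusted rate would show any remaining effect of incomplete follow-up.

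This changes data collection only, not who stops vaccination or why. The cost is about one sentence in each document and a few extra telephone contacts.

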## 7.2. Participant Discontinuation/Withdrawal From the Study

A participant may be withdrawn from the study at any time at the request of his/her parent(s)/legal guardian(s) or may be withdrawn at any time at the discretion of the investigator for safety, behavioral, compliance, or administrative reasons. Reasons for discontinuation from the study include the following:

- Adverse event;
- Death;
- No longer meets eligibility criteria;
- Protocol deviation;
- Physician decision;
- Study terminated by sponsor;
- Medication error without associated adverse event;
- Withdrawal by participant's parent(s)/legal guardian(s);
- Lost to follow-up;
- Other.

If a participant does not return for a scheduled visit, every effort should be made to contact the participant's parent(s)/legal guardian(s). All attempts to contact the participant's parent(s)/legal guardian(s) and information received during contact attempts must be documented in the participant's source document. In any circumstance, every effort should be made to document participant outcome, if possible.

At the time of discontinuing please refer to the ISF and [SoA](#) for assessments to be collected at the time of study discontinuation and follow-up and for any further evaluations that need to be completed.

The participant's parent(s)/legal guardian(s) should ideally notify the investigator in writing of the decision to withdraw consent from future follow-up, whenever possible. The participant's parent(s)/legal guardian(s) should be questioned regarding their reason for withdrawal. The investigator or his or her designee should capture the reason for withdrawal in the CRF for all participants.

The participant should be requested to return for a final visit, if applicable, and the investigator will perform the procedures indicated for the next visit. Any AEs or SAEs that are continuing at the time of withdrawal from the study should be followed until resolution or, in case of permanent impairment, until the condition stabilizes.

If a participant is withdrawn from the study, his/her parent(s)/legal guardian(s) may request destruction of any remaining samples, but data already generated from the samples will continue to be available, and may be used to protect the integrity of existing analyses. The investigator must document any such requests in the site study records and notify the sponsor accordingly.

If the participant is withdrawn from the study and his/her parent(s)/legal guardian(s) also withdraws consent (see [Section 7.2.1](#) for disclosure of future information), no further evaluations should be performed and no additional data should be collected. The sponsor may retain and continue to use any data collected before such withdrawal of consent.

When a participant is withdrawn from the study because of an SAE, the SAE must be recorded on the CRF and reported on the Vaccine SAE Reporting form.

Lack of completion of all or any of the withdrawal/early termination procedures will not be viewed as protocol deviations so long as the participant's safety was preserved.

